6.1.1. Adjustments for Covariates

The study is stratified by baseline HbA1c with country as a block factor; therefore, both stratification factors (baseline HbA1c $<8.5\%$ or $\geq 8.5\%$ and pooled country) will be fit in the corresponding statistical model as fixed effects for the non-HbA1c measurements unless otherwise stated. For analyses of HbA1c, the strata of baseline HbA1c will be replaced with the

covariate of baseline HbA1c. For other continuous variables other than some safety laboratory measures, a corresponding baseline measure will be added as a covariate.

6.1.2. Handling of Dropouts or Missing Data

6.1.2.1. Multiple Imputation Based on Retrieved Dropouts

The primary and key secondary continuous endpoints for the treatment-regimen estimands will adopt the below missing data imputation method.

All data including those collected after rescue and/or treatment discontinuation will be included in the analyses. The missing data will be imputed based on retrieved dropouts defined as patients who had their HbA1c value measured at Week 36 (Visit 9) in the same treatment arm and the same status of premature treatment discontinuation (yes, no). Thus, for patients who prematurely discontinue treatment, missing data will be imputed based on patients who prematurely discontinued study drug, continued in the study, and had their HbA1c value measured at Week 36 (Visit 9). For patients who did not discontinue study drug but are missing their HbA1c value at Week 36 (Visit 9) (due to missing that visit, for example) and continued in the trial on treatment, the missing data will be imputed based on patients with an HbA1c value measured at Week 36 (Visit 9) on treatment.

This differs in how retrieved dropouts were originally defined in the protocol, where all missing data were imputed based on patients who prematurely discontinued treatment but still had their measurements taken at the primary endpoint Week 36 (Visit 9). While every effort will be taken to ensure patients attend all scheduled protocol visits, it is possible that some patients will be unable to attend Week 36 (Visit 9) and thus have missing HbA1c data at the primary endpoint, but continue in the trial on treatment beyond the 36-week time point. Retrieved dropouts as defined in the protocol do not adequately cover this missing pattern. Under this revised definition, it is assumed that the most likely values of the missing data would have been, if available, best imputed by information from patients who at Week 36 (Visit 9) are similar in terms of both randomized treatment assignment and treatment completion status. If the absolute value of the imputed HbA1c change from baseline is $<-4.5\%$ or $>4.5\%$, that value will be set to -4.5% or 4.5% , respectively, to avoid unrealistic imputed values.

The pattern mixture model (PMM) depends on the probability mass function of possible missing data patterns, which would not be known a priori. This proposed multiple imputation may require post hoc changes after either of the DBLs to resolve any convergence issues due to the inadequate number of retrieved dropout patterns. The latter may lead to choosing a simpler imputation model, which may be subject to model misspecification on top of the unverifiable missing not at random (MNAR) assumption.

The proposed multiple imputation may require post hoc changes after database lock to resolve any convergence issues.

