5.2. Determination of Sample Size

Assuming a screen failure rate of 40%, approximately 3000 patients will need to be screened to attain approximately 1800 patients randomized to the 3 treatment groups (600 patients/group) in a 1:1:1 ratio for dulaglutide 4.5 mg, 3.0 mg, and 1.5 mg. Assuming 15% dropout rate, this will result in approximately 510 patients per arm completing 36 weeks of treatment (the primary endpoint).

The aforementioned sample size provides $\geq 80\%$ power to demonstrate superiority of at least 1 of the investigational dulaglutide doses (4.5 mg or 3.0 mg) to dulaglutide 1.5 mg with respect to the primary endpoint (change from baseline in HbA1c) at Week 36 (Visit 9). This sample size is calculated based on the assumption that there is a treatment difference (for either investigational dose) in HbA1c change from baseline of approximately -0.22%, a standard deviation (SD) of 1.1%, and a 2-sided alpha of 0.05.

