The treatment-regimen estimand is included as primary at the request of the US Food and Drug Administration (FDA). The efficacy estimand will be considered primary for all other purposes, and will be applied to all efficacy outcomes unless otherwise specified to demonstrate the effect of treatment and avoid confounding effects with other antihyperglycemic agents.

Each of the estimands will be tested at the full significance level of 0.05.

Analyses of safety parameters will be conducted for the Safety Population unless otherwise specified.

Countries with fewer than 10 randomized patients will be pooled for statistical analyses. Pooled country will be employed for all formal statistical model-based analyses as a block factor unless otherwise denoted.

Unless otherwise specified, all tests of treatment effects will be conducted at a 2-sided alpha level of 0.05, and confidence intervals (CIs) will be calculated at 95%, 2-sided. All tests of interactions between treatments and factors of interest will be conducted at a 2-sided alpha level of 0.10. Multiplicity adjustment will be performed among the hypotheses related to the primary and secondary efficacy endpoints.

The baseline visit will be Visit 3. For all variables, including HbA1c, if baseline data are not available or are missing, the last nonmissing measurement taken up to the first dosing date/time will be used for the baseline measurement. The efficacy measure for the primary analysis is defined as the change from baseline in HbA1c to Week 36 (Visit 9).

For all statistical analyses, missing data will be treated as missing at random for all analyses unless otherwise specified.

The treatment groups mentioned in this document are based on the randomized treatment groups: dulaglutide 4.5 mg, dulaglutide 3.0 mg, and dulaglutide 1.5 mg.

All efficacy and safety data will be summarized by each treatment group at each scheduled visit unless otherwise indicated. Dulaglutide 1.5 mg will serve as the reference treatment for treatment comparison in all efficacy analyses unless otherwise specified.

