6.9. Efficacy Analyses

6.9.1. Primary Efficacy Analysis

6.9.1.1. Primary Outcome and Methodology

There will be 2 primary estimands to compare each investigational dulaglutide dose and dulaglutide 1.5 mg in terms of the primary measure of HbA1c change from baseline to Week 36 (Visit 9). See Section 6.1.

For each type of estimand, the 2 investigational doses will be tested versus dulaglutide 1.5 mg simultaneously, controlling the 2-sided alpha of 0.05. Each of the estimands will be tested separately with a full 2-sided alpha of 0.05.

For the efficacy estimand, an MMRM will be employed as the primary analysis of on-treatment without rescue data described in Section 6.1.

For the treatment-regimen estimand, an ANCOVA model will be applied as the primary analysis to the complete data using multiple imputation (Section 6.1.2.1). The model terms include pooled country and treatment as fixed effects, and baseline HbA1c as a covariate. The estimates and standard errors from the imputed datasets will be pooled (Little and Rubin 1987). The inference will be made through the pooled estimates.

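### Read literally, the SAP's bound on imputed HbA1c change resets a fall of more than 4.5 points to a rise of 4.5; the likely effect is small and deleting one phrase cures it

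*SAP*

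**What the plan says.** SAP 6.1.2.1 sets out the multiple imputation and its scope: "The primary and key secondary continuous endpoints for the treatment-regimen estimands will adopt the below missing data imputation method". Missing Week 36 values are imputed from patients in the same arm with the same treatment-discontinuation status who have a Week 36 value.

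The section then adds a limit for HbA1c. The condition begins "If the absolute value of the imputed HbA1c change from baseline is" and continues with two alternatives, below -4.5% or above 4.5%. The consequence is that "that value will be set to -4.5% or 4.5" percent, "respectively, to avoid unrealistic imputed values".

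The imputed values feed a primary analysis. SAP 6.9.1.1 states: "For the treatment-regimen estimand, an ANCOVA model will be applied as the primary analysis to the complete data using multiple imputation". SAP 6.1 makes this estimand primary at the FDA's request.

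The limit appears nowhere else. SAP Appendix 1 summarises the imputation without it, and Protocol 10.3.3.1.2 contains no such bound.

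**The concern.** The condition is placed on an absolute value, but its two alternatives are signed. Applied exactly as written, the first alternative is empty. Every large imputed fall then satisfies the second, and because the resets are paired in order it becomes a large rise. A rule meant to remove implausible values would create them.

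The sentence changes data in the FDA-primary analysis, and it is the only specification of the bound. A programmer or an independent validator has no second statement to check it against.

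**Working it through.** **1. The plan's own figure.** SAP 5.2 assumes "approximately -0.22%, a standard deviation (SD) of 1.1%, and a 2-sided alpha of 0.05", with 600 x 0.85 = 510 completers per arm. The standardised difference is 0.22 / (1.1 x sqrt(2/510)) = 3.19. Power is Phi(3.19 - 1.960) = 0.891 at two-sided 0.05, and Phi(3.19 - 2.241) = 0.830 at the 0.025 that SAP 6.1.4 gives each dose. The stated 80% or more is reproduced. It does not depend on the bound.

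**2. The rule, coded both ways** (HbA1c percentage points).

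| Imputed change | As written | Limit on the signed change |
|---|---|---|
| -6.0 | +4.5 | -4.5 |
| -5.0 | +4.5 | -4.5 |
| -4.6 | +4.5 | -4.5 |
| -4.5 | -4.5 | -4.5 |
| -2.0 | -2.0 | -2.0 |
| +4.6 | +4.5 | +4.5 |

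The two readings differ only below -4.5, by 4.5 - (-4.5) = 9.0 points per affected value. One such value moves the mean of a 600-patient arm by 9.0/600 = 0.015 in that imputed data set.

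**3. Shift in one arm.** Inputs: SD s = 1.1 from SAP 5.2. Everything else is assumed: normal draws, mean change m, wider SDs, and 10% of the arm imputed.

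- Share of draws affected: P = Phi((-4.5 - m)/s)
- Arm-mean shift (literal minus intended): 0.10 x 9.0 x P

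| m | s | P | Shift |
|---|---|---|---|
| -1.2 | 1.1 | Phi(-3.00) = 0.13% | +0.001 |
| -1.2 | 1.4 | Phi(-2.36) = 0.9% | +0.008 |
| -1.2 | 1.7 | Phi(-1.94) = 2.6% | +0.024 |
| -1.6 | 1.7 | Phi(-1.71) = 4.4% | +0.040 |

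**4. Bias in the comparison.** A shift common to both arms cancels; only the difference matters. Take two arms with imputed means 0.22 apart, equal SDs and 10% imputed in each. The bias is 0.90 x (P at m - 0.22, minus P at m).

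| m | s | Between-arm bias |
|---|---|---|
| -0.8 | 1.1 | 0.90 x (0.00078 - 0.00038) = 0.0004 |
| -1.2 | 1.1 | 0.90 x (0.00256 - 0.00135) = 0.001 |
| -1.2 | 1.4 | 0.90 x (0.01390 - 0.00921) = 0.004 |
| -1.2 | 1.7 | 0.90 x (0.03501 - 0.02612) = 0.008 |
| -1.6 | 1.7 | 0.90 x (0.05746 - 0.04401) = 0.012 |

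The first and last rows are the extremes for m of -0.8, -1.2 and -1.6 with s of 1.1, 1.4 and 1.7. Against the planned 0.22, the largest is 0.012/0.22, about 5%.

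**5. Sensitivity to the assumptions.** For means from -0.5 to -2.0 and SDs from 1.1 to 2.0, the single-arm shift runs from 0.0002 to 0.143 with 15% imputed, and from 0.0001 to 0.048 with 5% imputed. If SDs differ between arms, the bias can exceed step 4. With m = -1.2 and 10% imputed in both arms, SD 1.7 against SD 1.1 gives 0.024 - 0.001 = 0.023, with a sign that depends on which arm has the wider draws.

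**The case against.** The strongest reply is that this is a drafting slip with one sensible reading. Two signed limits, two signed resets paired in order and the purpose "to avoid unrealistic imputed values" all point to a limit on the signed change. The word 'absolute' may have been meant to distinguish HbA1c percentage points from a relative percentage. A programmer would probably code the intended rule, and nothing in the documents shows that the literal one was or would be programmed. All of that stands. It settles how serious the point is, but the sentence is still wrong as written.

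Four stronger readings are tempting, and the documents do not support them.

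- **That the rule works against the better dose.** Patients who stopped study drug are imputed from same-arm patients who also stopped, and who should receive another glucose-lowering intervention (Protocol 7.7.5.4 and 8.1.1). Nothing says that their changes keep the dose order. Patients who missed Week 36 while on treatment might keep it, but they are imputed from on-treatment patients, a large donor group, so wide draws caused by few retrieved dropouts would not apply to them.
- **That a shift of 0.04 can be set against the planned 0.22.** The first is a shift in one arm and the second a difference between arms. Step 4 gives the like-for-like comparison.
- **That the rule inflates between-imputation variance.** This was not calculated, so no size can be given.
- **That the intended rule also fails, because a fall of 4.5 from the entry minimum of 7.5% leaves an HbA1c of 3.0%.** The 7.5% limit applies at Visit 1 (Protocol 6.1), whereas change is measured from Visit 3 (SAP 6.1). Limiting the change rather than the resulting value is a choice open to the sponsor.

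**Conclusion.** The point holds as a wording error in an operative rule of the FDA-primary analysis. Read literally, the lower limit never fires and an imputed fall of more than 4.5 points becomes +4.5%.

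At the plan's SD the effect is negligible: an arm-mean shift of about 0.001 with an assumed mean of -1.2% and 10% imputed. It becomes visible only with wide draws. SAP 6.1.2.1 itself allows that retrieved dropouts may be too few, so wide draws are possible, but the SDs above 1.1% used here are assumptions. With SDs up to 1.7%, the single-arm shift reaches about 0.04 at a mean of -1.6%, and the between-arm bias about 0.012. The latter rests on imputed means 0.22 apart, equal SDs and equal missingness; unequal SDs or missingness could give more. The direction of any bias cannot be stated from the documents.

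Sample size, power and alpha are unaffected. The point does not show that the analysis was run wrongly. Correcting it is desirable rather than critical.

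**What to change.** In SAP 6.1.2.1, delete 'the absolute value of', so that the test is on the signed change: an imputed change below -4.5% becomes -4.5%, and one above 4.5% becomes 4.5%. Confirm that the analysis code does this. Optionally, report the number of bounded draws per arm, which would show whether the limit mattered.

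The cost is one phrase in the SAP and a check of one line of code. Nothing else in the design or analysis changes.

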6.1.2.2. Other Imputation Methods

For analysis of patients achieving HbA1c target <7.0%, those who have missing data at Week 36 (Visit 9) will be imputed as not reaching the HbA1c target as a sensitivity analysis for the efficacy estimand. This, however, will be the primary analysis for the treatment-regimen estimand.

The LOCF method will be used to impute the missing endpoint data for the other binary efficacy endpoints such as HbA1c target and nonlongitudinal continuous variables up to Week 36 (Visit 9) and 6-point self-monitored plasma glucose (SMPG), β -cell function as measured by the Homeostasis Model Assessment-2 method (HOMA2-%B) and insulin resistance as measured by the HOMA2 method (HOMA2-IR), C-peptide, fasting insulin, fasting glucagon, and the selected safety laboratory measures.

Any missing component of date and/or time will be imputed following Lilly or dulaglutide compound level standards. For example, the missing day or month could be imputed with the first day of the month, or first month of the year.

If the first dosing date/time is missing, the nonmissing randomization date will be used to impute the first dosing date.

Other imputation may be applied if deemed necessary even after this document is approved. This addition or even change does not require an SAP revision. Rather, these detailed imputation rules will be documented.

6.1.3. Multicenter Studies

No analyses related to site are planned.

[figure not shown]
6.1.4. Multiple Comparisons/Multiplicity

To control overall Type 1 error, the graphical approach (Bretz et al. 2011) presented in [Figure GBGL.2](#) will be used to compare the treatment effect among the pre-defined parameters of interest to address the primary and the key secondary efficacy objectives defined in the protocol at Week 36 (Visit 9) for the ITT Population. In this figure, the overall significance level of 2-sided $\alpha=0.05$ will be equally split between H_1 and H_2 with 0.025 to H_1 and 0.025 to H_2 . H_5 to H_8 will only be tested if H_1 to H_4 pass. The number attached for certain edges denotes the proportion of the allocated fraction of α from a prespecified hypothesis (node), if it is confirmed, that will be passed to the next hypothesis.

This graphical approach will be conducted separately for each of the 2 estimands, and each will be tested at the full significance level of 0.05:

- Treatment-regimen estimand
- Efficacy estimand

The below graphical scheme may be revised per the observed correlation matrix using blinded data among the parameters of interest at Week 36 (Visit 9) prior to the primary DBL.

Abbreviations: D1.5 = once weekly dulaglutide 1.5 mg; D3.0 = once weekly dulaglutide 3.0 mg; D4.5 = once weekly dulaglutide 4.5 mg; FSG = fasting serum glucose; H = hypothesis; HbA1c = glycated hemoglobin A1c.

Figure GBGL.2. Graphical testing scheme for Study H9X-MC-GBGL.

- H₁*: Superiority test of dulaglutide 4.5 mg versus dulaglutide 1.5 mg in mean change from baseline in HbA1c at 36 weeks
- H₂*: Superiority test of dulaglutide 3.0 mg versus dulaglutide 1.5 mg in mean change from baseline in HbA1c at 36 weeks
- H₃*: Superiority test of dulaglutide 4.5 mg versus dulaglutide 1.5 mg in mean change from baseline in body weight at 36 weeks
- H₄*: Superiority test of dulaglutide 3.0 mg versus dulaglutide 1.5 mg in mean change from baseline in body weight at 36 weeks
- H₅*: Superiority test of dulaglutide 4.5 mg versus dulaglutide 1.5 mg in proportion of patients achieving an HbA1c <7.0% at 36 weeks

H_6 : Superiority test of dulaglutide 3.0 mg versus dulaglutide 1.5 mg in proportion of patients achieving an HbA1c <7.0% at 36 weeks

H_7 : Superiority test of dulaglutide 4.5 mg versus dulaglutide 1.5 mg in mean change from baseline in FSG at 36 weeks

H_8 : Superiority test of dulaglutide 3.0 mg versus dulaglutide 1.5 mg in mean change from baseline in FSG at 36 weeks

6.2. Patient Populations

Six patient populations are defined for the analyses in this study with detailed information listed in [Table GBGL.2](#). Unless otherwise specified, listings will include All Randomized Patients. Efficacy analyses will be conducted for the ITT Population, and safety analyses will be conducted for the Safety Population. The primary efficacy measure (change from baseline in HbA1c) will also be evaluated in the PP and Completers populations.

In all efficacy analyses, except for treatment-regimen estimands, all data after rescue and/or treatment discontinuation (Section 6.1) will be censored. Analyses of safety parameters will be conducted for the Safety Population including the postrescue therapy data unless otherwise specified.

Table GBGL.2. Populations for Analyses

Population	Description
Entered	All patients who sign informed consent
All Randomized	All patients who are randomized
Intent to Treat (ITT)	All patients who are randomized and take at least 1 dose of study medication for an assigned treatment arm ^a
Safety	All patients who are randomized and take at least 1 dose of study medication for the assigned treatment arm
Completers	All ITT patients who have an HbA1c measure at Week 36 (Visit 9), regardless of compliance with the protocol, rescue medication, or treatment discontinuation. However, data collected after rescue and/or treatment discontinuation will be excluded
Per Protocol (PP)	All ITT patients who meet all of the following criteria: 
 • Have no important protocol deviation that could impact the assessment of the primary endpoint (Section 6.8) • At least 75% compliant with study drug administration through Week 36 (Visit 9) • Complete the treatment period through 36 weeks (Visit 9) • Have a value of the primary efficacy measure (HbA1c) at Week 36 (Visit 9) excluding data collected after treatment discontinuation or initiation of new antihyperglycemic therapy

Abbreviation: HbA1c = glycated hemoglobin.

a Analyses using the treatment-regimen estimand will include all patients in the ITT population who have a baseline measurement for the parameter of interest, while analyses using the efficacy estimand will include patients in the ITT population who have a baseline and at least 1 postdose measurement for the parameter of interest.

6.3. Patient Disposition

The reasons for patient discontinuations from study treatment and from the study will be summarized for the All Randomized Population by treatment.

Kaplan-Meier curves by treatment for time to study treatment discontinuation due to any reason, and due to adverse event (AE) up to Week 36 (Visit 9) (primary DBL) or Week 52 (Visit 11) (final DBL) will be displayed separately. The log-rank p-value will be presented.

In addition, all entered patients will be summarized including, but not limited to, the total number of patients screened (entered) and the number of patients excluded due to screen failure. Patient disposition will be listed for the All Randomized Population.

6.4. Patient Characteristics

Demographic and baseline clinical characteristics will be summarized by treatment for the ITT, PP, and Completers populations separately. A Chi-square test will be used for treatment comparisons on categorical data analysis.

6.5. Concomitant Therapy

The prespecified concomitant medications of interest will be summarized by treatment for baseline and after randomization for the ITT Population. The concomitant therapies will be mapped using the World Health Organization Drug Dictionary in the clinical trial database and will be further classified using Anatomical Therapeutic Chemical (ATC) codes for reporting purposes.

The agents of interest for the summary report include the following groups of medication:

- antihyperglycemic agents
 - background metformin therapy
 - agents used for short-term therapy for acute condition (up to 14 days)
 - rescue therapy (only applicable after randomization)
 - agents initiated after permanent discontinuation of study drug (only applicable after randomization)
 - agents used for other reasons
- weight loss medications
- systemic glucocorticoids
- antihypertensive agents
- lipid-lowering agents
- antithrombotic agents
- anti-inflammatory agents

6.6. Treatment Compliance

Treatment compliance will be collected by sites using the compliance case report form (CRF). The compliance for each visit is defined as taking at least 75% of the scheduled injections of the study treatment for the period preceding that visit. Overall treatment compliance for each patient is defined as taking at least 75% of the injectable treatment for at least 75% of the nonmissing

visits, that is, the overall compliance percentage is at least 75% for this patient. The overall compliance in percentage for each patient will be calculated by taking the number of visits the patient was compliant divided by the total number of visits with nonmissing compliance data for this patient $\times 100$. Treatment compliance will be summarized descriptively by treatment using the ITT Population.

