8.1.2. Temporary Interruption of Study Treatment

In certain situations after randomization, the investigator may need to temporarily discontinue (interrupt) study drug (eg, due to an AE or a clinically significant laboratory value). If study drug interruption is due to an AE, the event is to be documented and followed according to the procedures in Section 9.2 of this protocol. Every effort should be made by the investigator to maintain patients on study drug and to restart study drug after any temporary interruption, as soon as it is safe to do so. See Section 7.2.1 for dosing details when resuming study drug after a temporary interruption. Investigators should inform the sponsor that study drug has been temporarily interrupted. The data related to temporary interruption of study treatment will be documented in source documents and entered on an eCRF.

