10.2. Populations for Analyses

Table GBGL.4 defines the populations to be used for analyses.

Table GBGL.4. Populations for Analyses

Population	Description
Entered	All participants who sign informed consent
All randomized	All patients who are randomized
Intent to treat (ITT)	All participants who are randomized and take at least 1 dose of study medication for an assigned treatment arm
Completers	All ITT patients who have an HbA1c measure at Visit 9 (Week 36) regardless of compliance with the protocol, rescue medication, or treatment discontinuation. However, data postrescue and/or posttreatment discontinuation will be excluded
Per protocol (PP)	All ITT patients who meet all of the following criteria: 
 • Have no important protocol deviation that could impact the assessment of the primary endpoint • At least 75% compliant with study drug administration through Week 36 • Complete the treatment period through 36 weeks (Visit 9) • Have a value of the primary efficacy measure (HbA1c) at Visit 9 (Week 36) • Excluding data collected postrescue and/or posttreatment discontinuation

Abbreviation: HbA1c = hemoglobin A1c.

Note: The full list will be defined in the Statistical Analysis Plan.

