10.3.2.4. Treatment Compliance

Treatment compliance is defined as taking at least 75% of required injections for the visit intervals (see Section 7.6). Overall compliance is defined as being at least 75% compliant with investigational product for at least 75% of visits across the Treatment Period. Compliance will be summarized by each treatment, and overall.

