Summary statistics for categorical measures will include number of subjects and percentages. The proportions of patients achieving target HbA1c $<7.0\%$ and $\leq 6.5\%$ at Week 36 (Visit 9) will be analyzed using a longitudinal logistic regression with repeated measurements. In this model, pooled country, treatment, visit, and treatment-by-visit interaction will be fit as fixed effects, and baseline HbA1c as a covariate. A logistic regression model will be applied for the aforementioned HbA1c target analysis at Week 36 (Visit 9) using LOCF by removing visit-related terms from the corresponding longitudinal logistic regression model.

For the analysis of other categorical measures, Fisher's exact test will be used for treatment comparisons unless otherwise specified. Categorical variables will be summarized by sample size and the number of patients and percentages for each treatment group at each visit. Imputed data may be applied in model-based data analyses, but will not be used in data listings. The latter will only present the non-imputed raw data, including site-reported scheduled and unscheduled visits, or early termination visit data; however, only scheduled visits for the measure of interest will be included in the summary table and statistical inference unless otherwise stated.

All statistical analyses will be conducted with SAS Version 9.4® or higher unless otherwise stated.

For primary DBL, all tables, figures, and listings (TFLs) will use the data up to Week 36 (Visit 9) or the study discontinuation date, whichever is earlier, unless otherwise specified.

For the final DBL delivery, TFLs will use the data up to the end of the treatment period (Week 52 [Visit 11]) or the study discontinuation date, whichever is earlier, unless otherwise stated.

Before each DBL, all key data will be reviewed. Any decision to exclude either subjects or observations from the statistical analyses will be made and documented by the study team, and will include the rationale.

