6.8. Important Protocol Deviations

Important protocol deviations will be summarized descriptively by treatment and listed for all randomized patients. All important deviations related to study inclusion or exclusion criteria, conduct of the trial, patient management, or patient assessment will be described. The rationale for choosing certain important protocol deviations as exclusionary from the PP Population will be based on their potential effect on the primary efficacy measure. The following protocol conditions as well as other conditions identified at the site and agreed upon by the study team may result in exclusion from the PP Population along with the criteria listed in [Table GBGL.2](#):

- informed consent was never obtained
- patients who are randomized but the informed consent date is missing
- patients who have an HbA1c $<7.5\%$ or $>11.0\%$ at study entry (Visit 1)
- patients who have known type 1 diabetes
- patients who had any hematologic condition that may have interfered with HbA1c measurement (for example, hemolytic anemias, sickle-cell disease)
- excluded medication:
 - weight loss agents if the duration of use is 14 days (cumulative) during the treatment period
 - any new glucose-lowering medication initiated after randomization at Visit 3 and prior to Visit 11 (end of treatment period) for >14 days, except for study drug, rescue therapy, glucose-lowering medications initiated after study drug discontinuation, or short-term use of insulin (≤ 14 days) for management of medical emergencies
 - >14 consecutive days' use of systemic glucocorticoid during the treatment period

- patients who have a missing HbA1c at baseline (both Visit 1 and Visit 3) or at 36 weeks (Visit 9)
- patients who do not have an overall compliance with study drug of at least 75% up to 36 weeks

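### Is the Per Protocol compliance criterion left without a single definition, so that membership depends on how it is programmed?

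*SAP*

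**What the plan says.** Protocol Table GBGL.4 (Section 10.2) lists among the Per Protocol criteria "At least 75% compliant with study drug administration through Week 36". SAP Table GBGL.2 (Section 6.2) repeats it, adding only the visit number. Neither bullet cites a compliance definition.

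The definition stands elsewhere. SAP 6.6 rates a visit compliant if at least 75% of the injections due since the previous visit were taken, and then states: "Overall treatment compliance for each patient is defined as taking at least 75% of the injectable treatment for at least 75% of the nonmissing" visits. It gives the formula as compliant visits over visits with a compliance record, times 100. Protocol 10.3.2.4 has the same two-level structure, "at least 75% compliant with investigational product for at least 75% of visits across the Treatment Period", and is silent on missing records.

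SAP 6.8 names a set of conditions that "may result in exclusion from the PP Population along with the criteria listed in" Table GBGL.2. The last of them is "patients who do not have an overall compliance with study drug of at least 75% up to 36 weeks".

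Two further provisions bear on the point. SAP 6.1 has key data reviewed before each database lock and says "Any decision to exclude either subjects or observations from the statistical analyses will be made and documented by the study team", with the rationale. Protocol 8.1.2 says of interruptions: "The data related to temporary interruption of study treatment will be documented in source documents and entered on an eCRF".

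**The concern.** Four features look troublesome together.

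- The bullet in the table can be read as a share of injections, and it does not point to 6.6. Protocol 10.3.2.4 encourages that reading, because it uses 75% compliant for the injection share and adds the visit share separately.
- The visit rule gives a 4-week interval the same weight as a 10-week one, so the two readings can classify a patient in opposite ways.
- The 6.8 wording is permissive, while the table requires every criterion to be met.
- Under the visit rule the one noncompliant interval allowed may be the longest and last, Weeks 26 to 36. Protocol 5.4 expects the full effect on plasma glucose after about 8 to 12 weeks of therapy and on HbA1c after about 12 to 24. A patient who took nothing in those ten weeks is an odd member of a set meant to reflect adherence at Week 36.

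At stake is the content of one robustness analysis of the primary endpoint (Protocol 10.3.3.1.1, SAP 6.9.1.2). If two programmers could build different Per Protocol sets, agreement or disagreement with the main result would be harder to interpret.

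**Working it through.** **Inputs.** Dosing is once weekly (Protocol Table GBGL.2). Compliance is assessed from Visit 4, and the visits up to the primary endpoint fall at Weeks 4, 8, 12, 18, 26 and 36 (Protocol Section 2). The documents give no injection count for this criterion, so there is no stated figure to reproduce. The counts below are derived and assume on-schedule visits and six nonmissing compliance records.

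| Interval ending at Week | 4 | 8 | 12 | 18 | 26 | 36 | Total |
|---|---|---|---|---|---|---|---|
| Doses due | 4 | 4 | 4 | 6 | 8 | 10 | 36 |
| Fewest doses giving at least 75% | 3 | 3 | 3 | 5 | 6 | 8 | 28 |

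**Injection reading.** 0.75 × 36 = 27 doses.

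**Visit rule (SAP 6.6).** 4/6 = 66.7% fails and 5/6 = 83.3% passes, so one noncompliant visit is allowed.

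- Lowest passing total: the minimum in five intervals and nothing in the last, 28 − 8 = 20, or 20/36 = 55.6%.
- Highest failing total: two visits must be noncompliant. The smallest loss that makes a visit noncompliant is 2 doses (2 of 4, or 4 of 6), so 36 − 2 − 2 = 32, or 32/36 = 88.9%.

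**Opposite classifications.**

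| Doses by interval | Total | Compliant visits | Visit rule | Injection reading |
|---|---|---|---|---|
| 4, 4, 4, 6, 8, 0 | 26/36 = 72.2% | 5/6 | pass | fail |
| 4, 0, 0, 6, 8, 10 | 28/36 = 77.8% | 4/6 | fail | pass |

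**Sensitivity.** Moving Visits 7 to 9 by up to a week either way shifts the lowest passing total to 19–21 and the highest failing total to 31–33, out of 35–37 doses. With one compliance record missing, the lowest passing total is 28 − 8 − 6 = 14: nothing taken in the Week 36 or Week 26 interval, one of the two unrecorded and the other the single noncompliant visit allowed out of five.

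**Would another rule protect the last interval?** At most 36 − 10 = 26 doses precede Week 26, so the injection reading forces only 27 − 26 = 1 of the last 10. Requiring the Week 36 interval itself to be compliant would force 8 of 10 and raise the lowest passing total to 28 − 6 = 22 (61.1%), the failed interval then being the 8-dose one.

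**Which definition applies.** The 6.8 bullet speaks of overall compliance of at least 75%. SAP 6.6 defines overall compliance, attaches the same 75% to it and gives the formula. Table GBGL.2 itself refers to 6.8 in its deviation criterion. Protocol 7.6 defines compliance by visit interval, and Protocol 10.3.2.4 builds the overall measure from visits. No section defines a percentage of injections pooled to Week 36. The window is not in doubt either: both tables and 6.8 fix it at Week 36, so the whole-Treatment-Period wording in Protocol 10.3.2.4 does not govern this criterion.

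**Permissive or mandatory.** The 6.8 list works alongside the table, and the table requires all of its criteria. A patient who fails the compliance criterion is out by the table, whatever discretion 6.8 allows.

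**The case for a change.** The strongest case for acting is that a robustness population should not depend on inference. The compliance bullet in the table carries no pointer, although the bullet above it cites 6.8. The 6.8 bullet does not cite 6.6 by number. The classifications do differ in both directions, and a cross-reference costs one phrase. The case of no doses in Weeks 26 to 36 is possible: the protocol states no maximum length for an interruption, and Protocol 7.6 keeps poorly compliant patients in the study.

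The missing pointer and the arithmetic stand. They show imperfect editing and an unweighted rule with wide extremes. They do not show two competing definitions, because only one is written down. The cross-reference would record what an analyst would do anyway.

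The last-interval case stands as a possibility but is narrow. The patient must not have discontinued study drug, because Table GBGL.2 also requires completion of treatment through Week 36 and a Week 36 HbA1c not taken after discontinuation or new antihyperglycemic therapy. The gap would have to be a recorded interruption or plain missed doses, and it would have to survive the documented pre-lock review, where SAP 6.8 lets the team act on a deviation's potential effect on the primary measure. Protocol 5.4 gives the time to full effect and says nothing about how fast effect is lost after missed doses.

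A last-interval condition is a legitimate choice, but it is a trade-off. It selects harder on behaviour after randomization, which may itself depend on how well each dose is tolerated.

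**Conclusion.** No change is needed. The Per Protocol compliance criterion is best read as overall compliance under SAP 6.6, calculated over Visits 4 to 9; SAP 6.8 uses that term with the Week 36 window. The table's missing pointer is a drafting gap that analysts fill sensibly. The nonmissing-visit denominator is an ordinary operational detail that Protocol 10.3.2.4 left open.

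The visit rule is coarse: 20 of 36 doses can pass and 32 of 36 can fail, against 27 of 36 for a pooled share. These are extremes under weekly dosing, on-schedule visits and complete records, and the 20-dose case also needs the bare minimum in every other interval. Replacing the rule with a pooled threshold would still ask for only 1 of the last 10 doses, so it would not secure exposure just before the endpoint.

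The consequence is confined to one supportive analysis. Both primary estimands and the graphical testing procedure use the ITT Population (SAP 6.1, 6.1.4), and the Completers analysis, the other population check, has no compliance condition. No effect on any result has been shown, and the documents do not allow the number of affected patients to be estimated.
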